#### **Sample Size Estimate:**

The sample size is not based on statistical considerations. Subjects who are proptosis non-responders at Week 24 of HZNP-TEP-301 or who were proptosis responders at Week 24 but meet the criteria for re-treatment due to relapse during the Follow-Up Period of HZNP-TEP-301 will be eligible for enrollment.

## 2.1 Schedule of Assessments

	Open-Label Treatment Period  (24 Weeks)											Follow-Up Period  (24 weeks)		Follow-Up Contact  (48 Weeks)				
	1	2	3	4	5	6	7	8	9	10	11/ PW 	FU1	FU2	FU3/ PW 	FU4	FU5	FU4	FU5
Study Visit																		
Week (W)/ Month (M)	Day 1 	W1	W3	W4/ M1	W6	W9	W12/ M3	W15	W18	W21	W24/ M6	W28/ M7	W36/ M9	W48/ M12	W48/ M12	W72/ M18	W72/ M18	W96/ M24
Visit Window (± days)	(+14) 	(±1)	(±3)	(±1)	(±3)	(±3)	(±3)	(±3)	(±3)	(±3)	(±7)	(±7)	(±7)	(±7)	(±14)	(±14)	(±14)	(±14)
Subject response in Study HZNP-TEP-301	Proptosis Non-responder or Relapse											Proptosis Non-responder Only		Relapse Only	Proptosis Non-responder Only			
Informed Consent	X																	
Review inc/exc criteria	X																	
Weight 	X 						X					X		X	X			
Study drug infusion 	X		X		X	X	X	X	X	X								
Phone (email) contact for safety 24 hours postdose 	X		X															
Investigator assessment of active disease	X				X		X		X			X	X	X	X			
Efficacy assessments																		
CAS	X 				X		X		X			X	X	X	X			
Clinical Measures of Severity - includes proptosis, diplopia, and motility restriction	X 				X		X		X			X	X	X	X			
Safety assessments																		
Pregnancy Test 	X 		X		X	X	X	X	X	X	X	X	X	X				
Physical exam 	X 	X			X		X		X			X 			X 			
Ophthalmic exam 	X 	X			X		X		X			X			X			
Vital Signs 	X 	X	X	X	X	X	X	X	X	X		X	X	X	X			
12-Lead ECG	X 		X		X		X					X			X			
Clinical laboratory tests 																		
Chemistry (excl. glucose)	X 		X		X	X	X		X			X		X	X			
Thyroid (FT3, FT4, TSH) 	X 		X		X	X	X		X			X		X	X			
Hematology	X 	X	X	X	X	X	X	X	X	X		X	X					

Study Visit	Open-Label Treatment Period  (24 Weeks)											Follow-Up Period  (24 weeks)			Follow-Up Contact  (48 Weeks)			
	1	2	3	4	5	6	7	8	9	10	11/ PW 	FU1	FU2	FU3/ PW 	FU4	FU5	FU4	FU5
Week (W)/ Month (M)	Day 1 	W1	W3	W4/ M1	W6	W9	W12/ M3	W15	W18	W21	W24/ M6	W28/ M7	W36/ M9	W48/ M12	W48/ M12	W72/ M18	W72/ M18	W96/ M24
Visit Window (± days)	(+14) 	(±1)	(±3)	(±1)	(±3)	(±3)	(±3)	(±3)	(±3)	(±3)	(±7)	(±7)	(±7)	(±7)	(±14)	(±14)	(±14)	(±14)
Subject response in Study HZNP-TEP-301	Proptosis Non-responder or Relapse											Proptosis Non-responder Only			Relapse Only		Proptosis Non-responder Only	
Glucose 	X 	X	X	X	X	X	X	X	X	X	X		X	X				
HbA1c	X 						X					X		X	X			
Urinalysis	X 		X		X	X		X			X		X	X				
ADA/NAb samples 	X 		X		X						X 		X	X				
AE, SAE assessment 	X 	X	X	X	X	X	X	X	X	X	X	X	X	X				
Concomitant medications	X 	X	X	X	X	X	X	X	X	X	X	X	X	X				
GO-QoL Questionnaire	X 			X		X					X	X		X				
PK samples 	X	X	X	X		X					X 							
Contact (phone/email) to assess additional TED treatment 															X	X	X	X

ADA=anti-drug antibody; AE=adverse event; CAS=Clinical Activity Score; ECG=electrocardiogram; FT3=free triiodothyronine; FT4=free thyroxine; FU=Follow-Up; GO-QoL=Graves' Ophthalmopathy Quality of Life Questionnaire; HbA1c=glycated hemoglobin; M=month; NAb=neutralizing antibody; PK=pharmacokinetic; PW=premature withdrawal; SAE=serious adverse event; TED=thyroid eye disease; TSH=thyroid stimulating hormone; W=week.

Footnotes:

- Open-label Treatment Period. Subjects with TED who are proptosis non-responders at Week 24 of HZNP-TEP-301 or were proptosis responders at Week 24 but who meet criteria for re-treatment due to relapse during the Follow-Up Period in HZNP-TEP-301 are eligible to enroll and receive 8 infusions of teprotumumab (10 mg/kg for the first infusion titrated to 20 mg/kg for the remaining infusions) in an open-label fashion.
- Proptosis non-responders from Study HZNP-TEP-301 will participate in a 6-month Follow-Up Period; subjects who relapsed during the Follow-Up Period of HZNP-TEP-301 will not participate.
- Proptosis non-responders from Study HZNP-TEP-301 who complete the Month 12 Visit and subjects who relapsed during the Follow-Up Period of HZNP-TEP-301 and complete the Week 24 Visit will be contacted via phone or email by research staff to enquire if any treatment for TED has been received since last study contact.
- If subjects wish to discontinue study drug during the open-label Treatment Period, subjects will return for a clinic visit and undergo the Week 24 assessments, except for PK and ADA evaluations. Subjects who were proptosis non-responders at Week 24 of HZNP-TEP-301 will be encouraged to continue study participation in the Follow-Up Period.
- If a subject wishes to prematurely discontinue from the study during the Follow-Up Period, he/she will return for a clinic visit and undergo the Month 12 assessments prior to discharge.
- On Day 1 (Baseline), subjects will receive the first dose of study drug; however, Baseline assessments will be performed prior to dosing.

7. Day 1 will occur within 14 days after the final visit of Study HZNP-TEP-301 (Week 24 for proptosis non-responders and up to Week 72 for subjects who relapse).
8. Dosing will be adjusted if there is a change in weight during the Treatment Period. The weight obtained at Week 12 can be used in dose calculations beginning at Week 12 or Week 15.
9. If Day 1 of the extension study occurs on the same day as the final visit of HZNP-TEP-301 (Week 24 [or PW1] for proptosis non-responders and Week 72 [or PW2] for subjects who relapse), assessments do not need to be repeated, and the final assessments from the lead-in study will serve as the Baseline assessments for the extension study.
10. Subjects will receive teprotumumab 10 mg/kg on Day 1 followed by 20 mg/kg q3W for the remaining 7 infusions.
11. Phone (or email) contact by research staff focusing on safety and tolerability aspects will be made the day after infusion for the first and second infusions, and thereafter as deemed appropriate. In addition, subjects who experience an infusion-associated event after any subsequent infusion will also be contacted by phone (or email) by research staff the day after the infusion, and thereafter as deemed appropriate.
12. Perform urine pregnancy tests prior to dose (as applicable) for female subjects of childbearing potential (including those with an onset of menopause <2 years prior to Baseline of HZNP-TEP-302, non-therapy-induced amenorrhea for <12 months prior to Baseline of HZNP-TEP-302, or not surgically sterile [absence of ovaries and/or uterus]).
13. Physical exam will include assessment of presence or absence of pretibial myxedema on Day 1 and Week 24/PW of the Treatment Period and Month 12/PW of the Follow-Up Period. If present, measurements of instep and calf will be taken.
14. Ophthalmic exam: best corrected visual acuity, pupil exam, color vision assessment, Ishihara color plates (or equivalent) or related red desaturation, intraocular pressure, and slit lamp exam. If significant abnormalities are noted compared to previous visits, including a loss of 2 lines or more of vision, development of pupil abnormalities including APD, rise in intraocular pressure, development of corneal infiltrates or other abnormalities not here specified but of concern to the ophthalmologist, further investigations of visual function will be conducted according to the ophthalmologist decision.
15. Vital signs (heart rate, blood pressure, respiratory rate, temperature) will be measured at all clinic visits. Vital signs will be measured pre- and post-infusion on Day 1 and Week 3, and pre-dose on all other infusion days. Additional vital signs will be monitored if infusion-associated AEs occur (see [Section 9.5.4.3](#) for details).
16. Non-diabetic subjects should be fasting at Weeks 1 and 4 only. Diabetic subjects should be fasting at each visit blood glucose is evaluated.
17. ALT/AST must be  $\leq 3$  x the upper limit of normal (ULN) and serum creatinine must be  $< 1.5$  x the ULN (according to age) at the most recent clinic visit to be eligible for enrollment.
18. Subjects must be euthyroid with the baseline disease under control or have mild hypo- or hyperthyroidism (defined as free thyroxine [FT4] and free triiodothyronine [FT3] levels < 50% above or below the normal limits) at the most recent clinic visit. Every effort should be made to correct the mild hypo- or hyperthyroidism promptly and to maintain the euthyroid state for the full duration of the clinical trial.
19. HbA1c must be < 9.0% at the most recent clinic visit. If the HbA1c is elevated and considered clinically significant at any time point after Baseline, it will be repeated approximately every 45 days until it returns to normal or the baseline value.
20. If a sample is positive in the ADA test, after confirmatory and reactive titer testing, the sample will then be tested for NAb. If the subject tests positive for NAb, he/she will be followed until levels either revert to Baseline or the subject's value decreases or remains stable. Any subject with a positive NAb test at Week 48 (or PW) during the Follow-Up Period will continue to be followed until the subject's value decreases or remains stable.
21. Not collected for subjects who prematurely discontinue from the open-label Treatment Period.
22. Adverse events that are ongoing at completion of HZNP-TEP-301 and/or occur prior to dosing on Day 1 will be considered pre-dose AEs. Adverse events occurring or worsening after the dose on Day 1 through the end of the Treatment Period will be considered treatment-emergent AEs (TEAEs). Adverse events occurring or worsening during the Follow-Up Period will be considered postdose AEs. All SAEs that occur from the signing of informed consent through 30 days after study discontinuation will be recorded.
23. PK samples will be collected prior to, and at the end of, the infusion on Day 1 and Weeks 3 and 9 of the open-label Treatment Period; additional single samples will be collected at Weeks 1, 4, and 24.
24. If TED treatment has been received since last contact, the subject will be questioned regarding type of treatment and outcome/response.

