### **9.3.3 Removal of Subjects from Therapy or Assessment**

All subjects are free to withdraw from study participation at any time, for any reason, and without prejudice to their further medical care. In addition, the Investigator may terminate a subject from the study at any time. The primary reason for discontinuation from the study and/or study drug should be recorded on the eCRF using one of the following categories:

- Adverse Event. The subject experiences an AE that imposes an unacceptable risk to the subject's health, or the subject is unwilling to continue because of an AE. AEs requiring permanent study drug discontinuation per the protocol include:
  - A drug-related anaphylactic reaction.
  - A persistently severe drug-related AE that does not abate to mild or moderate intensity at least 2 weeks prior to the next scheduled dose.
  - Severe drug-related hyperglycemia (e.g., blood glucose > 250 mg/dL) that does not abate to mild or moderate intensity with anti-diabetic treatment (dose may be skipped up to 2 times prior to permanently discontinuing study drug; see [Section 9.4.6.3.2](#) for details).
  - Diagnosed or suspected IBD (e.g., diarrhea with or without blood or rectal bleeding associated with abdominal pain or cramping/colic, urgency, tenesmus, or incontinence for more than 4 weeks without a confirmed alternative diagnosis OR

endoscopic or radiologic evidence of enteritis/colitis without a confirmed alternative diagnosis).

- Lack of Efficacy. Removal of a subject from the study is at the discretion of the Investigator and may occur if the Investigator determines that study drug administration is not benefitting the subject and eye symptoms linked to progressing disease worsen posing an unacceptable risk to the subject. The specific care of the subject is best determined by the Investigator and managing physician(s) involved in the subject's care and may require removal from the study. All subjects are free to withdraw from study participation at any time, for any reason, allowing them to receive any specific treatment for TED that is considered necessary per their treating physician and local standard of care.
- Non-Compliance with Study Drug/Other/Protocol Deviations. The subject has a significant protocol deviation, does not comply with study drug administration schedule, or fails to adhere to other study requirements as stated in the protocol.

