#### **9.4.6.3.2 Dose Modifications, Interruptions, and Delays**

Subjects will be monitored for immediate infusion-associated events (e.g., nausea, vomiting, facial flushing, warmth, dyspnea, dizziness, hypertension, hypotension, pruritus) and delayed infusion-associated events (e.g., rash). If immediate infusion-associated events are noted, the infusion rate will be slowed or interrupted, symptomatic treatment (e.g., antipyretics, antihistamines, beta-agonists, oxygen, IV fluid) will be administered, and vital signs (temperature, blood pressure, pulse, and respiratory rate) will be monitored every 5 minutes until stable and then every 15 minutes for 2 additional determinations. The infusion may be restarted upon complete resolution of symptoms; however, study drug dosing will be permanently discontinued if the event is an anaphylactic reaction.

If delayed infusion-associated events are noted, subjects may continue dosing at the Investigator's discretion; however, if a rash worsens following repeated dosing or other signs of serum sickness (e.g., delayed fever, myalgias, arthralgias) are present, study drug dosing will be permanently discontinued.

Following the appearance of either immediate or delayed infusion-associated events, subsequent doses may be pre-treated with diphenhydramine (1 to 1.25 mg/kg IV; maximum of 50 mg), ranitidine (50 mg IV), famotidine (0.5 mg/kg IV), dexamethasone (0.4 mg/kg IV; maximum of 20 mg), and/or acetaminophen (500 mg). All subsequent infusions will be administered over approximately 90 minutes (but not less than 80 minutes) with vital signs monitored every 15 minutes from the start of the infusion through 60 minutes after infusion completion.

In general, the decision to continue dosing should take into consideration the potential benefit and risk to a subject.

Any severe drug-related AE must revert to mild or moderate in intensity at least 2 weeks prior to the next scheduled dose in order for the dose to be administered; if the AE remains severe in intensity within 2 weeks of the next scheduled dose, the subject will be withdrawn from treatment.

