### **9.5.3 Pharmacokinetic Measurements**

Blood samples will be collected in 5 mL serum separator tube (SST) collection tubes to evaluate PK at the following time points: pre- and post-infusion on Day 1 and Weeks 3 and 9 of the Treatment Period; single samples will also be collected at Weeks 1, 4, and 24 (but not PW) of the Treatment Period. Samples will be collected, processed, and stored at  $\geq -70^{\circ}\text{C}$  at the site until shipment to the central laboratory. [REDACTED] will store the samples at  $\geq -70^{\circ}\text{C}$  until shipment to [REDACTED] for PK testing (see [Table 6.1](#)).

Instructions for processing, handling, storing and shipping of PK samples will be detailed in a laboratory manual that will be provided to each site prior to site initiation. A central laboratory will be used for PK sample analysis.

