#### 9.5.4.7 Immunogenicity Testing

Blood samples will be collected in a 5 mL SST collection tube for immunogenicity testing (ADA and possibly Neutralizing Antibodies [NAb]) from all subjects prior to dosing on Day 1, prior to dosing on Weeks 3 and 9, and at Week 24 of the Treatment Period, and Months 9 and 12 (or PW) of the Follow-Up Period. Samples will be collected, processed, and stored at  $\geq -70^{\circ}\text{C}$  at the site until shipment to the central laboratory [REDACTED] will store the samples at  $\geq -70^{\circ}\text{C}$  until shipment to [REDACTED] for immunogenicity testing. If a subject tests positive for ADA after confirmatory and reactive titer testing, the sample will then be tested for NAb. If the subject tests positive for NAb, he/she will be followed until levels either revert to Baseline or the subject's value decreases or remains stable. Any subject with a positive NAb test

at Month 12 (or PW) of the Follow-Up Period will continue to be followed until the subject's value decreases or remains stable.

Instructions for processing, handling, storing, and shipping of immunogenicity samples will be detailed in a laboratory manual that will be provided to each site prior to site initiation.

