#### **9.5.6.11 Week 24/Premature Withdrawal – Treatment Period**

Week 24 is the final visit of the Treatment Period. Study drug is not administered.

- Obtain blood samples for hematology and chemistry (including thyroid, glucose, and HbA1c) analysis (see [Section 9.5.4.6](#) for details concerning test results and study participation).
- Collect urine sample for urinalysis and also for a pregnancy test for females of childbearing potential.
- Collect blood sample for immunogenicity testing (only subjects who complete the Treatment Period, not those who prematurely discontinue study drug administration).
- Collect blood sample for PK analyses (only subjects who complete the Treatment Period, not those who prematurely discontinue study drug administration).
- Enquire about signs and symptoms and concomitant medications throughout the visit.
- Perform 12-lead ECG.
- Perform physical and ophthalmic examinations, including vital signs.
- Measure weight.
- Perform efficacy assessments (CAS, Clinical Measures of Severity including proptosis, diplopia and motility restriction).
- Administer GO-QoL questionnaire.

Subjects who were proptosis non-responders in Study HZNP-TEP-301 will enter the Follow-Up Period and will be instructed to return to the clinic in one month for the first follow-up visit. Subjects who relapsed during the Follow-Up Period of HZNP-TEP-301 and chose to enter this extension study will not participate in the Follow-Up Period.

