10.4. IMMUNOGENICITY

Serum samples will be collected prior to dose at Day 1, Weeks 3, 9, 24, 36 and 48 (or PW). If a subject tests positive for ADA after confirmatory and reactive titer testing, the sample will then be tested for neutralizing antibody (NAb). If the subject tests positive for NAb, he/she will be followed until levels either revert to Study Baseline or the subject's value decreases or remains stable.

Immunogenicity endpoints include:

- Incidence of ADA and NAb (out of positive ADA samples, if applicable) by visit and provided by treatment received in HZNP-TEP-301

The count and percent of subjects will also be provided by treatment received in HZNP-TEP-301 for the following:

- Overall positive ADA result, defined as at least one confirmed positive antibody
- Cumulative negative ADA result, defined as negative ADA results at all time points for a subject
- A negative ADA on HZNP-TEP-302 Day 1 and a positive result at any post-dose visit

Immunogenicity sampling times and results will be listed.

Further, the mean and CV% (calculated as $100\% \times SD/mean$) of pre-dose serum concentrations will be provided by visit in the subset of subjects who are confirmed ADA positive, NAb positive (if applicable) and ADA negative for each visit. This analysis will be provided for the PK Population.

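### No anti-drug antibody or PK sample is scheduled at the Treatment Period premature-withdrawal visit, so subjects stopped for hypersensitivity have no scheduled post-stop antibody draw in that period, and relapse subjects have none later

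*Protocol*

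**What the plan says.** **Sampling.** Protocol 9.5.4.7 schedules ADA "prior to dosing on Day 1, prior to dosing on Weeks 3 and 9, and at Week 24 of the Treatment Period", then at Months 9 and 12 (or premature withdrawal, PW) of Follow-Up. PK is drawn before and at the end of the infusion on Day 1 and Weeks 3 and 9. Protocol 9.5.3 adds that "single samples will also be collected at Weeks 1, 4, and 24 (but not PW) of the Treatment Period".

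**Early stoppers.** In Protocol 2.1, footnote 4 says that on stopping study drug "subjects will return for a clinic visit and undergo the Week 24 assessments, except for PK and ADA evaluations". Footnote 21, attached to the Week 24/PW cell of the ADA and PK rows, reads "Not collected for subjects who prematurely discontinue from the open-label Treatment Period". SAP Table 1 repeats both footnotes. Protocol 9.5.6.11 agrees for ADA: "Collect blood sample for immunogenicity testing (only subjects who complete the Treatment Period, not those who prematurely discontinue study drug administration"), and it has a matching line for PK.

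**Stopping rules.** Protocol 9.3.3 lists "A drug-related anaphylactic reaction" among the events that end study drug permanently. Protocol 9.4.6.3.2 does the same "if a rash worsens following repeated dosing or other signs of serum sickness" appear.

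**After the stop.** Non-responders from the lead-in study are encouraged, not required, to continue into Follow-Up. Relapse subjects have no Follow-Up Period (Protocol 9.3.3).

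**Analysis.** SAP 10.4 gives the schedule as "Serum samples will be collected prior to dose at Day 1, Weeks 3, 9, 24, 36 and 48 (or PW") without saying which period's PW visit is meant. It then counts subjects as overall ADA-positive, cumulatively ADA-negative, or negative on Day 1 and positive later.

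**The concern.** Immunogenicity is a safety endpoint (SAP 4.5) and infusion reactions are events of special interest. Subjects who received teprotumumab in the lead-in study are re-exposed here, for up to 8 + 8 = 16 infusions. If such a subject is stopped for a hypersensitivity reaction, antibody status and drug level after the reaction are what one would want to see. The plan omits the draw at the visit where they could be obtained, and the reason for the omission is the stop itself. The resulting missingness depends on how treatment was tolerated, and the SAP has no rule for it. Follow-up of neutralizing antibody (NAb) is triggered only by a sample that was taken, so it cannot start from a result that first turns positive after the stop.

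**Working it through.** The plan states no figure to reproduce. The check sets the infusion calendar against the ADA calendar, in nominal weeks.

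**Inputs.** Infusions: Weeks 0 (Day 1), 3, 6, 9, 12, 15, 18, 21 (Protocol 9.1). ADA in the Treatment Period: pre-dose at Weeks 0, 3 and 9, and Week 24 for completers only (9.5.4.7, 9.5.6.11). ADA in Follow-Up: Weeks 36 and 48, non-responders only.

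**Formulas.** For a reaction at infusion week w: age of last result = w − (latest ADA week ≤ w). Wait to the next scheduled draw, for a non-responder who enters Follow-Up = 36 − w, assuming Month 9 stays at Week 36 from Day 1.

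| Reaction at infusion of | Last ADA draw (pre-dose) | Age, weeks | Infusions since that draw, this one included | Weeks to Month 9 draw |
|---|---|---|---|---|
| Day 1 | Day 1 | 0 | 1 | 36 |
| Week 3 | Week 3 | 0 | 1 | 33 |
| Week 6 | Week 3 | 3 | 2 | 30 |
| Week 9 | Week 9 | 0 | 1 | 27 |
| Week 12 | Week 9 | 3 | 2 | 24 |
| Week 15 | Week 9 | 6 | 3 | 21 |
| Week 18 | Week 9 | 9 | 4 | 18 |
| Week 21 | Week 9 | 12 | 5 | 15 |

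Three of the eight infusions (Day 1, Weeks 3 and 9) have a same-day pre-dose ADA sample, plus pre-dose and end-of-infusion PK. Five have none. After a stop at any row, the number of scheduled ADA draws left in the Treatment Period is 0. Beyond it, a relapse subject has 0. A non-responder has 2 (Months 9 and 12) on completing Follow-Up, a Follow-Up PW draw on leaving it early, or 0 if Follow-Up is not entered. If Follow-Up is timed from the PW visit instead of Day 1, Month 9 comes about 3 months after that visit.

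**Effect on the SAP 10.4 counts.** Take a relapse subject who is ADA-negative at Day 1, Week 3 and Week 9 and is stopped for a reaction at Week 15. No sample is positive, so the subject is neither overall positive nor Day 1-negative/post-dose-positive. All available results are negative, so the subject is cumulatively negative. The latest supporting sample is 15 − 9 = 6 weeks older than the reaction. SAP 10.4 sets no minimum number of samples and no rule for early stoppers.

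**Effect on the concentration summaries.** The SAP 10.4 table by ADA status uses pre-dose concentrations. Pre-dose PK exists only at Day 1 and Weeks 3 and 9 (SAP 9), which footnote 21 does not touch. The direct PK loss is the Week 24 concentration.

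**Would a PW sample reach the tables?** Not reliably. SAP 6.4 assigns a PW visit to the nearest scheduled visit. Days 75–158 map to Weeks 12–21, none of which has an ADA row. Days 54–74 map to Week 9, where an existing scheduled result takes precedence and the PW result is not summarized.

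**The case against.** The exclusion is deliberate and consistent across the protocol and SAP Table 1. It removes one draw, in a subset whose size is unknown. A PW sample would fall at a varying time after the last dose and would not be directly comparable with the Week 24 sample. Many listed reasons for stopping have nothing to do with antibodies: hyperglycemia, inflammatory bowel disease, lack of efficacy, non-compliance, pregnancy. In TED01RV, infusion-associated events occurred in 1 of the 43 teprotumumab subjects, and the protocol describes those seen with the drug to date as not anaphylactic. Listings of immunogenicity, concentrations and events of special interest are already planned for all subjects. No PW draw helps with a subject lost to follow-up.

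Most of this stands as a limit on size. It also rules out several stronger readings that a reader might infer:

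- *Early stoppers give no ADA or PK data.* They give every sample due before the stop.
- *There is never a sample at the reaction.* On Day 1 and at Weeks 3 and 9 there is a pre-dose one. A delayed reaction that is dosed through can also be followed by a scheduled draw.
- *Relapse subjects are never sampled.* They lack only a scheduled sample after the stop. A subject already NAb-positive is followed further, and unscheduled samples are not forbidden.
- *The number affected equals all discontinuations, enriched for hypersensitivity.* No figure supports this, and non-responders in Follow-Up are sampled again.
- *The concentration-by-ADA table is biased.* It rests on pre-dose samples that are largely unaffected.
- *Every subject is re-exposed.* Lead-in placebo subjects meet the drug here for the first time.

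None of this supplies a post-stop ADA result for a subject stopped for hypersensitivity, and the sections reviewed give no reason for the omission.

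**Conclusion.** The point holds in this limited form. After a stop for anaphylaxis, worsening rash or signs of serum sickness, no ADA draw is scheduled in the rest of the Treatment Period. For relapse subjects none is scheduled afterwards; for non-responders it depends on entering Follow-Up. For reactions at Weeks 12 to 21 the last scheduled result is 3 to 12 weeks old, and the SAP 10.4 classifications can rest on pre-reaction samples alone. The direction and size of any effect on ADA incidence cannot be computed, because the documents give no count of early stops. No efficacy endpoint is involved, so this is a worthwhile safety-data improvement and not a threat to the study's main result.

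Three assumptions matter. Weeks are nominal. A reaction at Week 21 is at the last infusion, and the documents do not say whether that subject counts as a completer and keeps the Week 24 draw. The outcome also depends on which stopping text governs: Protocol 7.1.3.4.5.5.1 has subjects with anaphylaxis leave the study and allows removal for serum sickness, while 9.4.6.3.2 permanently stops dosing for both. If subjects leave the study, non-responders lose the Follow-Up draws too. These sections must be reconciled.

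**What to change.** Draw ADA and PK at the Treatment Period PW visit and record the time since the last dose.

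- **Protocol 2.1 and SAP Table 1:** delete footnote 21 and the PK/ADA exception in footnote 4.
- **Protocol 9.5.6.11 and 9.5.3:** remove the completer-only limits and the PW exclusion.
- **Protocol 9.5.4.7:** add the PW visit to the Week 24 draw.
- **SAP 10.4:** state which PW visits are meant. Use the PW sample in the overall-positive, cumulative-negative and Day 1-negative/post-dose-positive classifications, whatever visit SAP 6.4 assigns it to. Count early stoppers with no post-stop sample separately and not as cumulative negatives.
- **Protocol 7.1.3.4.5.5.1 and 9.4.6.3.2:** reconcile them on leaving the study versus stopping drug.

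With this change, scheduled post-stop ADA draws go from 0 to 1 for relapse subjects who attend the PW visit. For non-responders they go from 2 to 3 with full Follow-Up, or from 0 to 1 without it. The cost is two 5 mL tubes and the assays, at a visit where hematology and chemistry blood is already drawn, plus an amendment and laboratory-manual wording. The drawback is a variable interval since the last dose, hence the need to record it. If sampling can no longer be changed, the separate count in SAP 10.4 is still possible.
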